well as any necessary covariates, including cocaine positive vs negative urine tests prior to random assignment as a covariate. Generalized linear mixed models (GLMM) will be used to analyze repeated measures data, since this technique can include participants with incomplete data without resorting to imputation. This approach has been found to minimize bias and maximize power in cases of incomplete follow-up (see Hedden et al, 2009). Data will then be examined using the nonbinary method described by McCann and Li (2012) in which participants who meet an end of study threshold of success (1 week EOS abstinence) are assigned values indicating their number of beyond threshold weeks of success (in our case 1-24). This distribution will be analyzed as a function of drug condition using a two-sided Vander Waerden two-sample test (Permutt and Berger, 2000).

All other analyses will be conducted in the overarching group that includes those abstinent and actively using at baseline. This approach will allow us to preserve all study Aims with a reduced sample size that will ensure the study can be completed in the time allowed.

The data analysis plan consists of the following:

- 1) Comparison of groups for baseline differences. Participants will be compared as a function of medication group on baseline characteristics to determine whether they are comparable with respect to general demographic features, baseline drug use, and reinforcement measures (drug vs. money relative reinforcing potency scale, Snaith-Hamilton Pleasure scale). Groups will be compared using t tests for continuous measures and chi-square tests for categorical characteristics. If medication groups are found to differ on baseline measures, then these characteristics will be used as covariates in subsequent analyses assessing treatment effect.
 - 2) Primary outcome analyses: (see above)
- 3) Secondary outcome analyses: The main secondary outcome measure will be biochemically-confirmed abstinence from opiates. We hypothesize that participants receiving bupropion will have a higher proportion of opiate abstinent samples as well as for cocaine. Analyses conducted to assess the treatment effect for opiate use will be identical to those used for cocaine use (described above).
- 4) Other Secondary Outcome Analyses: Other secondary outcomes are reinforcement measures, such as the drug vs. money relative reinforcing potency scale, the Snaith-Hamilton Pleasure scale, as well as time engaging in non-drug-related activities and changes in neurocognitive performance. These measures will be collected at baseline and throughout the study. Analyses will be the same as those described for cocaine (GEE with medication group X time as factors). Participants receiving bupropion are hypothesized to find non-drug activities to be more reinforcing than participants receiving placebo, and to engage in more of them.
- 5) Exploratory mediation analysis. Measures collected at baseline including demographic characteristics, intake drug use severity, non-drug reinforcement, non-drug activities and neurocognitive performance will be examined separately to determine whether any predicts outcome independently of treatment. Next, we will add each of these measures to the models that assessed treatment effect, used for primary outcome analyses. If the treatment effect becomes diminished by addition of a third variable, this will be considered preliminary evidence that the third variable may mediate the effect of the treatment.

7. Risks

- a. Medical risks, listing all procedures, their major and minor risks and expected frequency.
- b. Steps taken to minimize the risks.
- c. Plan for reporting unanticipated problems or study deviations.
- d. Legal risks such as the risks that would be associated with breach of confidentiality.
- e. Financial risks to the participants.

Bupropion XL is an FDA-approved antidepressant and smoking cessation pharmacotherapy and will be used in accordance with the prescription labeling instructions during this study. The extended release (XL) preparation allows for once-daily dosing and thus improved adherence. The medication will be titrated to an oral dose of 300 mg after 3 days at 150 mg daily. With a half-life of 21 hours, steady state is

reached after 8 days. Methadone maintenance is a long-standing and effective usual care treatment for opioid dependence but does not directly impact the concurrent use of stimulants alcohol or other drugs.

Risks associated with Bupropion XL side-effects

Major risks of bupropion are summarized below; a complete list of potential side-effects is included in the consent form.

Allergic reactions. Participants may experience allergic reactions to bupropion characterized by a rash, itching, swelling of the face, mouth, and throat. Allergic reactions are rare but can be life-threatening and can cause trouble breathing (anaphylactic reaction). Participants will be informed of this risk and instructed to stop taking the study medication and immediately contact medical staff if they experience any swelling or tingling in the mouth, develop a rash, or observe swelling, redness and/or peeling of the skin.

Seizures. The most relevant risk of bupropion is dose-dependent seizures, especially at doses higher than those proposed for this study (e.g. 450 mg daily). Bupropion is contra-indicated in patients with a seizure disorder, in those taking other medications containing bupropion, those taking monoamine oxidase A inhibitors (MOA-AI, e.g., phenelzine, risk of hypertensive crisis due to enhanced norepinephrine release), and those undergoing abrupt cessation of alcohol or sedative-hypnotic medications. These risks are managed by appropriate exclusion criteria and close medical monitoring described below.

Cardiovascular effects. While generally safe for use even in people with cardiovascular disease, review of the literature suggests that bupropion may increase blood pressure slightly.

Other side-effects and drug accumulation. Other side-effects associated with Bupropion XL include anxiety, agitation, insomnia, vivid or abnormal dreams, and weight loss. Less common side-effects include headache, hypertension, constipation, flatulence, nausea. All of these will be monitored during the study. Drug accumulation can occur in cases of severe liver disease and renal insufficiency. Patients with transaminases > 3 x ULN and an eGFR < 30 mL/min are excluded from participation.

Neuropsychiatric risks: The risk of suicidal thinking and behaviors, including completed suicide has been associated with antidepressants especially in children, adolescents, and young adults (< 25 yrs). The population targeted in this study may include young adults. While the incidence of neuropsychiatric symptoms among patients taking bupropion is of serious concern, it is expected to be rare. All participants will be closely monitored for any changes in mood, thought disturbance or agitation.

Potential drug-drug interactions: There is a general risk that Bupropion might have an adverse reaction with other medications, including methadone. The main causes of drug-drug interactions with bupropion are due to induction or inhibition of CYP2B6 dependent enzymatic pathways and potentiation of norepinephrine availability by MAO-A inhibitors.

Alcohol interaction. Bupropion may decrease tolerance for alcohol and high alcohol intake may enhance metabolism of bupropion through Interaction with CYP2B6 dependent enzymatic pathways. Drug interactions are also found with ritonavir, nelfinavir and efavirenz, Highly Active Antiretroviral Therapy drugs (HAART), with a reduction in the activity of HAART and/or a reduction in bupropion concentration (Robertson SM et al, 2008). Pre-clinical studies demonstrate acute exacerbation of bupropion toxicity by the non-selective MAOI phenelzine, most likely due to increase in norepinephrine release mediated by MAO-A. These potential interactions are handled by excluding participants taking HAART medications or MAO inhibitors and by monitoring alcohol intake.

Methadone interaction. Bupropion is unlikely to influence methadone metabolism: five studies of bupropion in methadone maintenance context showed no adverse reactions as a result of bupropion administration in conjunction with methadone and/or cocaine use (Poling et al., 2006 & 2007; Margolin et al., 1990 & 1995, Levin FR et al., 2006).

Risks associated with methadone maintenance

This study will not be experimentally manipulating methadone doses and usual clinic policies and medical oversight will determine methadone doses. Methadone maintenance is associated with some risks including over sedation and QT prolongation. Any complaints of over-sedation will be evaluated by medical staff and methadone dose adjusted accordingly.

Other study-related risks

Diversion of study medication

Take-home doses of Bupropion XL will be provided for days when patients are given take-home (TH) methadone medication according to clinic policy. These will be for the most part single day TH on holidays, and for patients' unforeseeable emergencies. There is a small potential risk that study participants will divert or attempt to abuse the medication. However, bupropion is a Schedule V medication and is not associated with significant abuse liability. The limited take-home dosing and low abuse potential pose minimal risk of diversion.

Continued abuse of illicit drugs

Many participants who are enrolled in MM continue to abuse illicit drugs, and continued cocaine abuse is the targeted behavior of this study. Although there is no specific pharmacological risk of using cocaine and Bupropion concurrently, use of cocaine (or other illicit drugs) while enrolled in MM treatment is strongly discouraged and will be addressed by counselors during the study. Bupropion could affect the rate of cocaine and other drug use and this will be monitored as part of the study. Money or tangible goods earned in the contingency management program could supply funds for drug purchase. This is no different from the danger associated with funds secured in any other fashion. However, the process is self-limiting in contingency management since submission of a positive urine test immediately stops the dispersal of incentive payments.

Removal to controlled environment

Participants may experience a gap in research participation due to a period of non study-related hospitalization or incarceration. These individuals may be able to re-enter the research. However, such events will be handled on an individual basis according to best clinical judgment, and will take into account the safety and tolerability of inducting the participant back onto the study medication, the ability of the participant to resume reasonable compliance with the study requirements, and any marked changes in baseline cocaine use following the incident.

Pregnancy

There is a possibility that female participants may become pregnant while enrolled in the study and taking methadone and bupropion. Methadone is approved for use among pregnant women.while bupropion XL has been assigned to pregnancy category C where potential risks must be balanced by potential benefits in prescribing the medication. Urine pregnancy tests will be administered at 6-week intervals during the study as part of the health assessment. Study participation will be stopped for any woman who becomes pregnant.

Legal risks: Breach of confidentiality

Although staff members are highly trained to maintain participant confidentiality, there is always a risk that some of the confidential information collected could be revealed to people who are not involved in the research study. This could be embarrassing or risky to the participant and confidentiality breaches are considered to be very serious and are guarded against by standard precautions that include using only study ID's on CRF's and in data bases, using adequate password protection for data stored on computers and keeping identifying information (e.g. consent forms and PHI) in locked cabinets accessible only to research staff.

Financial risks. Participants who earn more than \$600 in the study may have this income reported to the IRS (pending IRB approval of an exception for drug abuse-related research at the BPRU).

Risks Management

Risks inherent in exposure to the study medication, Bupropion XL, are managed first by application of appropriate study exclusion criteria that minimize risk, second by on-going in-person monitoring of study participants by methadone nursing and/or research staff and third by periodic administration of questionnaires that address changes in mood and suicidal ideations including assessment 1-2 weeks after starting study medication, which is a critical time for emergence of neuropsychiatric symptoms. Participants will be evaluated during the 6-week baseline phase of the protocol for excessive alcohol or sedative use. If medical staff judges that continued use of alcohol or sedatives is unsafe for interaction with bupropion, the individuals study participation will be terminated prior to randomization. Blood pressure will be monitored at baseline, 1-2 weeks after medication starts and at 6-week intervals

thereafter. Blood pressure criteria for medication adjustment or discontinuation would be as per clinical guidelines, i.e, BP > 140/90. Naturally, we will also be alert to any other cardiovascular adverse events as well with clinical judgment being used to determine dose adjustment or medication discontinuation.

In addition, study participants will receive periodic (e.g. every 6 weeks) assessment, for the presence of inter current health problems and for new concurrent medications that may pose a risk of drug-drug interactions. No specific laboratory monitoring is recommended for patients on bupropion. Participants will not be allowed to take any other antidepressants while they are on the study and will be discharged from the study if they need to begin taking any excluded medications that pose a risk of drug-drug interaction.

Experienced research, counseling, nursing, and medical staff will be readily available on-site as needed to assess and manage AE's and SAE's and research staff will be trained to report any responses indicating risk to medical and/or nursing personnel immediately for review and follow-up. Medical staff will evaluate participants who report clinically significant side effects possibly related to Bupropion (e.g., headache, agitation, insomnia) or who experience neuropsychiatric symptoms (e.g. depression, agitation). A code to break the drug blinds is available 24/7 if needed in response to a medical emergency. A participant may be put on close monitoring and/or referred for treatment if warranted in the judgment of medical staff. A participant may also be promptly withdrawn from the study protocol if medical staff indicates it is in the best interest of the patient. In all cases of persistent complaints, referral or study withdrawal, the case will be followed by medical staff until the complaint is resolved and the incident will be fully documented in study records and reported to IRB and NIDA.

Responsibility for monitoring data and safety during this clinical trial resides with the Principal Investigator (PI) [name] and co-investigator [name], M.D. AE's and SAE's are generally discovered through careful and frequent monitoring of participants by research and clinical staff using open-ended questions about how the participant has been feeling recently. Any complaint is probed for information about frequency, duration and severity, coded on a side-effects checklist and described in a written summary report. The Principal Investigator coordinates the preparation of semi-annual summary reports on the prevalence of side effects and adverse events observed during the course of the study. These reports will be provided annually to the local IRB and to the NIDA Program Official with the annual progress report. The PI will also be responsible for promptly notifying in writing the local Institutional Review Board if a serious adverse event (SAE) occurs. A SAE is defined as either: death; a life-threatening occurrence; hospitalization; new onset significant medical disorder; or significant exacerbation of an existing medical disorder.

In addition an independent panel of consultants will be contracted for bi-annual review of the risks-benefits ratio of the study. At mid-point during enrollment (when 100 randomized participants have completed the study) this panel will be provided with reports of adverse events and with participant outcome data (urine sample results) by unlabeled medication groups (A vs. B), as a function of study assignment (relapse prevention vs abstinence initiation). This information will be used to assess whether the risks reported are considered to be of unusual magnitude or frequency across any specific groups and to determine whether the study should be ended prematurely due to participant safety concerns. It is unlikely that such a small study would be interrupted because of an uneven distribution of adverse events experienced by any one group, however we will ensure that a qualified panel of reviewers makes this decision.

9. Benefits

a. Description of the probable benefits for the participant and for society.

Study participation will directly benefit participants by providing them with methadone maintenance for opioid dependence, with increased urine monitoring beyond that available in usual care and with contingency management that is likely to reduce the amount of cocaine they use.

The study will provide important information about the efficacy of bupropion XL for reducing cocaine use in the context of methadone maintenance and background contingency management. The results of this study will provide valuable scientific information regarding the effects of dopamine systems activation on the saliency of non-drug monetary and non-monetary reinforcers as alternative to drug reinforcers. Study findings could also have direct clinical application for combined behavioral and pharmacological treatment of cocaine dependence should the hypotheses be borne out.

10. Payment and Remuneration

Detail compensation for participants including possible total compensation, proposed bonus, and any proposed reductions or penalties for not completing the protocol.

Each participant can earn \$50 for screening, \$210 for 6 longer assessment visits, and up to \$688 in abstinence-contingent incentives based on cocaine negative urine screens for a total of \$948 maximum earnings per participant. Participants can also earn Baltimore City Bus Tokens or be offered other incentives for attendance and/or other study related activities. There are no completion bonuses. Partial payment for study non-completers would be disbursed based on study assessments completed and contingent incentives earned.

11. Costs

a. Detail costs of study procedure(s) or drug (s) or substance(s) to participants and identify who will pay for them.

Participants may be required to pay treatment costs according to policies of the clinical performance site. All research-related costs including study medication and placebo, urine testing and abstinence incentive costs will be supported by the research grant. Any up-front fees associated with new participants entering ATS methadone treatment will be covered by the study.

Literature cited

American Psychiatric Association. (2013). Diagnostic and statistical manual of mental disorders (5th ed.). Arlington, VA: American Psychiatric Publishing.

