Placebo is included for scientific validity in a clinical trial needed to answer study questions related to medication efficacy.

f. Definition of treatment failure or participant removal criteria.

There is no clear definition of treatment failure for this study sample of methadone maintained patients since long-term methadone maintenance is standard care for their chronic relapsing disorder. Patients could potentially be dismissed from treatment for violating clinic rules particularly those relating to violence, firearms possession, drug sales or or other unacceptable behavior at the clinic. Participants could be removed from the study if severe or persistent medication side-effects were observed or if new medical conditions developed including pregnancy or concomitant medications were started that made their continued participation unsafe.

g. Description of what happens to participants receiving therapy when study ends or if a participant's participation in the study ends prematurely.

Study participants will continue on usual care methadone maintenance treatment at their normal methadone clinic after the study or in the event of premature withdrawal from the study.

Study Procedures: Urine Testing. Primary outcomes will be based on qualitative (pos/neg) urinalysis testing results using standard detection cut-off values. In order to detect recent use of cocaine, urine samples will be collected three times per week on non-consecutive days throughout the study, usually on Mon, Wed, and Fri. Sample collection will be observed if possible and all samples will additionally be tested for temperature and adulterants. A second sample will be requested if the original sample fails these tampering tests.

Study Procedures: CM Lead-In. Participants will enter the study following an intensive screening during which eligibility is determined, informed consent is signed and baseline assessment is completed. The study itself begins with a 6-week contingency management lead-in during which vouchers can be earned for submission of cocaine negative urine samples under an escalating schedule with reset to the original value in the case of missing or positive urines. A participant who stops cocaine use on the first day of the study and remains continuously cocaine abstinent would earn \$145 by the end of week 6. However, many participants may start earning later than week 1 or experience resets and thus earn less.

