Neurocognitive assessment. A battery of tasks designed to measure neurocognitive performance has been developed at the BPRU (Mintzer and Stitzer, 2002) and will be adapted for this study. Functions to be tested include psychomotor speed/pattern recognition (e.g. digit symbol substitution), set shifting/conceptual flexibility (e.g.; trail making tests), divided attention, long-term/episodic memory (e.g. recognition and free recall) and short-term/working memory and focused attention (e.g. N-back task). The Conners Continuous Performance Test will also be used to assess performance in areas of inattentiveness, impulsivity, sustained attention, and vigilance (Epstein et al., 2002).

Inclusion/Exclusion Criteria

Inclusion Criteria:

- Over 18 years old
- Enrolled or meets federal requirements for enrollment in methadone maintenance treatment, and willing to visit the clinic daily
- Evidence of current cocaine dependence (DSM-5 criteria, self-report, urine test positive for cocaine during the intake process or by clinical record during the past 3 months).
- · Willingness to swallow a capsule daily
- Willing to provide observed urine samples three times a week and participate in assessment procedures

Exclusion Criteria:

- Any history of epilepsy or seizure, including alcohol-, sedative-, or cocaine-related seizure;
- Any increased risk of seizure such as serious head trauma with a loss of consciousness of more than an hour duration, brain tumor, or other brain pathology increasing risk of seizure.
- · Current eating disorder including anorexia or bulimia
- Current use (last 30 days) of medication that is contraindicated with bupropion or other bupropion products (e.g. antidepressants, antipsychotics, MAO-A inhibitors, theophyllines, systemic steroids, etc)
- Allergy to bupropion or budeprion
- Liver enzymes greater than 3x ULN
- · Uncontrolled diabetes mellitus, or h/o diabetic coma
- Uncontrolled hypertension with BP > 140/90
- Current psychiatric diagnosis: schizophrenia, psychosis, major depression, mania, current suicidal ideation as determined by MINI psychiatric interview, cognitive impairment severe enough to preclude informed consent or valid responses on questionnaires
- Severe renal insufficiency (eGFR < 30 ml/min)
- Pregnancy or current breast feeding,

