- Medical illness that in the view of the investigators would compromise participation in research, such as uncompensated congestive heart failure, recent history of myocardial infarction (<1year), or urologic conditions that inhibit urine collection.
- Advanced HIV infection requiring the use of HAART, or with CD4 T cell < 200/uL

5. Drugs/ Substances/ Devices

- a. The rationale for choosing the drug and dose or for choosing the device to be used.
- Justification and safety information if FDA approved drugs will be administered for non-FDA approved indications or if doses or routes of administration or participant populations are changed.
- c. Justification and safety information if non-FDA approved drugs without an IND will be administered.

Bupropion was selected as the best candidate medication for this trial based on prior evidence for its synergistic interaction with contingency management to enhance treatment outcomes for substance users (Poling et al., 2006; Gray et al., 2010), recent positive findings from a laboratory drug versus money choice study by Stoops et al. (2012) and feasibility of use in clinical practice including low cost and low risk for significant side effects. Dose selection (300 mg/day) is based on clinical guidelines, safety considerations and prior research in substance users. Selection of the slow release dosage form supports feasibility and compliance by allowing the majority of dose ingestions to be observed at the clinic.

We believe use of this medication is exempt from IND application requirements under CFR 312.2 as the study is not intended to provide data that would influence indications, labeling or advertising. Further, The investigation involves a standard dose (300mg/day) and route of administration (oral). Neither the dose, route of administration, study population or other factors significantly increases the risks (or acceptability of the risks) associated with use of this product.

6. Study Statistics

- a. Primary outcome variable.
- b. Secondary outcome variables.
- c. Statistical plan including sample size justification and interim data analysis.
- d. Early stopping rules.

Sample size and power.

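### The risk section says participants taking HAART are excluded, but the eligibility list words its only HAART criterion by HIV stage or CD4 count, so a HAART user with non-advanced HIV is not plainly excluded

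*Combined protocol and SAP*

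**What the plan says.** Section 7 (Risks), in the paragraph on alcohol under potential drug-drug interactions, names ritonavir, nelfinavir and efavirenz as HAART drugs that interact with bupropion, "with a reduction in the activity of HAART and/or a reduction in bupropion concentration". It then gives the control: "These potential interactions are handled by excluding participants taking HAART medications or MAO inhibitors and by monitoring alcohol intake". No HIV stage or CD4 count is attached.

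The eligibility list in Section 4 (Inclusion/Exclusion Criteria) has two lines that could put this control into effect:

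- The HIV line: "Advanced HIV infection requiring the use of HAART, or with CD4 T cell < 200/uL".
- The medication line, which covers drugs contraindicated with bupropion taken in the last 30 days and gives as examples "e.g. antidepressants, antipsychotics, MAO-A inhibitors, theophyllines, systemic steroids, etc". No antiretroviral is named.

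Two provisions apply after entry. Section 4f allows removal if "concomitant medications were started that made their continued participation unsafe". Risks Management in Section 7 provides for periodic review of new concurrent medications and for discharge of anyone who has to begin an excluded interacting drug. The same subsection makes the exclusion criteria the first means of managing bupropion's risks.

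**The concern.** The two sections use different tests. Section 7 asks whether the person is taking HAART. The HIV line in Section 4 asks about disease stage or CD4 count. A screener works from the eligibility list, so if the list is narrower than the rule it is meant to carry out, the control that Section 7 relies on may not operate.

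The possible harm is the one the protocol itself describes: weaker HAART activity, lower bupropion concentration, or both. The planned assessments include no CD4 or viral-load monitoring, and Risks Management states that bupropion calls for no specific laboratory monitoring. A loss of HAART activity might therefore go unnoticed by study procedures.

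**Working it through.** The plan gives no figure to reproduce and no statistical calculation applies. The check is to take one participant through every provision that could exclude them.

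**Test case:** HIV not advanced, CD4 of 200/uL or more, on HAART at entry.

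| Provision | Met on a literal reading? |
|---|---|
| Section 4, HIV line, first limb | No: the infection is not advanced |
| Section 4, HIV line, CD4 limb | No: CD4 is not below 200/uL |
| Section 4, medication line | Not on its face: no antiretroviral is named, and Section 7 calls HAART interacting, not contraindicated |
| Section 4, medical-illness line | Not plainly: it is discretionary and concerns illness, not medication |
| Section 4f, removal | Not aimed at this case: it concerns medications started later |
| Section 7, Risks Management | Not aimed at this case: it concerns new medications or those a participant has to begin |
| Section 7, interaction paragraph | Yes: the person is taking HAART |

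Only the risk narrative plainly excludes this person.

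**Which wording closes the gap.** At CD4 of 200/uL or more, take two stages (advanced, non-advanced) and two treatment states (taking HAART; requiring it but not taking it). That gives 2 × 2 = 4 cases.

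- Current HIV line, literal reading: excludes the two advanced cases and misses the non-advanced person on HAART. Total 2 of 4.
- Current line plus a separate current-use exclusion: 2 + 1 = 3 of 4, with none lost. The fourth case (non-advanced, requiring but not taking HAART) lies outside the Section 7 rule, which concerns people taking it. The on-study provisions would apply if HAART were started.
- Current-use exclusion in place of the HIV line: excludes the two people on HAART but loses the advanced person who requires HAART and is not taking it. Total 2 of 4. The existing line should therefore stay.
- Current HIV line, with requiring HAART read as the marker of advanced disease: 4 of 4, and no gap.

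These are counts of logical cases, not estimates of how many participants fall in each.

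**The case against.** The strongest reply is that the HIV line already means what Section 7 says. The protocol does not define advanced infection separately, so a screener has only two working markers, HAART and CD4. Other lines pair a label with a marker in the same way, for example "Severe renal insufficiency (eGFR < 30 ml/min", where the eGFR value defines severe. On that pattern anyone who requires HAART counts as advanced, and Section 7 confirms the intent. This reading is plausible and probably what was intended. But the list does not state it, and two careful screeners could decide differently.

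The second reply is that the medication line would catch the case. It is open-ended, and its examples include antipsychotics, theophyllines and systemic steroids, which the seizure paragraph of Section 7 does not list as contraindicated. So the line uses the term broadly, and the screening medical exam in Section 4b gives staff a chance to notice HAART. This stands in part: a screener might well include antiretrovirals, but the text does not assure it.

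Third, the discharge rule can already be read to cover HAART, because Section 7 treats it as excluded. That is fair, but the rule still concerns drugs begun on study, not a regimen present at entry.

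A reader might also infer that HAART is the one exclusion in the risk section that was carried badly into the eligibility list. The documents do not support that. Section 7 says "Patients with transaminases > 3 x ULN and an eGFR < 30 mL/min are excluded from participation". The liver criterion matches closely ("Liver enzymes greater than 3x ULN"), but the renal criterion adds a severity word too, and Section 7 excludes MAO inhibitors where the medication line names only MAO-A inhibitors. A tally of matched and unmatched exclusions would depend on how strictly one compares them, and it would measure no harm.

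**Conclusion.** The inconsistency is real but minor. It rests on reading advanced infection as a condition separate from requiring HAART; on the other reading it disappears. It merits correction because the eligibility list is the protocol's first safety control and the sponsor's own rule is broader than the line meant to enact it.

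Its size cannot be estimated. The documents give no HIV or HAART prevalence and do not say how many people with non-advanced HIV and CD4 of 200/uL or more take HAART.

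Two stronger conclusions are tempting. One is that the protocol knowingly admits HAART users; Section 7 shows the opposite intent, and nothing shows that any were enrolled. The other is that lowered bupropion concentrations would dilute the treatment effect; without a prevalence or the size of the interaction, the documents give no basis for a claim about the endpoint, model or power.

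**What to change.** Keep the HIV line as it stands, so that people with advanced infection who require HAART but are not yet taking it remain excluded. Add a separate exclusion, for example: *HAART or any other antiretroviral medication taken in the last 30 days, at any stage of HIV.* Do not insert it among the examples in the medication line, because that would label HAART as contraindicated with bupropion, a status the documents never give it.

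State that this is an excluded medication for the discharge rule in Risks Management, so that HAART started on study is clearly covered. Ask study medical staff to review any enrolled participant who is on HAART.

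The cost is one added line. The medication criterion already requires a check of the last 30 days, so no new procedure is needed. The eligible pool may shrink slightly, which matters a little because Section 6 reports recruitment difficulty and a target cut from 200 to 100. But Section 7 already describes these people as excluded.
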